4.5. Study Arms

4.5.1 Attention control

Via the Way to Health platform, all patients will receive daily text messages that inform them their previous day's step count.

4.5.2. Automated Coaching Plus Gamification Intervention

Similar to patients randomized to the attention control arm, patients in the intervention arm will receive daily text messages that inform them whether they did or did not meet their step goal. In addition, they will receive biweekly text messages including encouragement to walk for exercise, reminders about their goal step increase, reminders about optimal practices for home-based walking in patients with PAD, and information about the benefit of exercise in improving PAD symptoms and functional capacity.

Patients randomized to the intervention arm will have a 4-week ramp-up towards their step goal. The net difference between baseline and their goal will be divided by 4 and the participant will be asked to achieve the 25% increase each week for the 4-week ramp-up and then maintain the step goal for the remaining study period. For example, a participant with a baseline of 5000 steps and goal of 7400 steps will be asked to achieve goals of 5600 steps in week 1, 6200 in week 2, and so on through the 4-week period. We have found that the rate of goal attainment is high using this gradual approach rather than encouraging the participant to go from 5,000 to 7,400 steps immediately. Following the ramp-up period, the participant will be asked to maintain their goal during the remainder of the study.

Other components of the gamification intervention are as follows:

- 1) Pre-commitment: First, each participant signs a pre-commitment contract agreeing to try their best to achieve their daily step goal. Pre-commitment has been demonstrated to help motivate behavior change.
- 2) Points: At the start of each week, the participant will receive 70 points (10 for each day that week). Points are endowed rather than given after goal achievement to leverage loss aversion – a concept from prospect theory that reveals that individuals are more motivated by losses than gains. Each day the participant is informed of their step count. If the step goal was achieved, he or she retains their points. However, each day the goal is not met, they are informed that they lost 10 points. Points are replenished at the start of the week to leverage the “fresh start effect” – the concept that individuals are more motivated for aspirational behavior around temporal landmarks such as the start of the week.
- 3) Levels: At the end of the week, if the participant has 40 points or more, he or she will advance one level. The levels include: blue (lowest), bronze, silver, gold, platinum (highest). If he or she has less than 40 points, he or she will drop down one level at the end of the week. This creates a sense of achievable goals (goal gradients) and uses loss aversion to help motivate ongoing efforts to not lose status. Each participant begins the intervention in the silver level. By starting them in the middle, the higher levels seem within reach and they will feel a sense of loss from dropping

down a level in the first week if they don't achieve 40 points; this may motivate them to initiate greater activity. After 8 weeks, we will reach out to individuals that are stuck in lower levels of blue or bronze and restart them back at silver. This allows for another "fresh start" and creates a new endowment effect as someone who is already at the bottom would otherwise not be able to drop down further and experience loss aversion. At the same time, we will also inquire if he or she would like to adjust their step goal as long as they are within the range of a 33% to 50% increase. In previous studies, we've found that some individuals set overly ambitious goals at the start of the intervention and that for participants who have trouble achieving their initial goals, we can re-engage them if goals are reset to a more reasonable level.

4) Supportive sponsor: Each participant will select a family member or friend of their choice who will serve as a supportive sponsor. This person will receive a weekly email with the participant's progress including accumulated points, level in the game, and average step count. This supportive sponsor will help to enhance social incentives to motivate the individual towards his or her goal. We will encourage participants to select someone with whom he or she comes into frequent contact and is close to such as a partner, family member, or friend that they see often. Prior to starting in the study, we will conduct a three-way phone call with the participant and their supportive sponsor. We will provide an overview of study procedures for their arm assignment, and then prompt the participant and supportive sponsor to discuss ways in which they can help the participant meet their step goals. At least 3 goals will be decided upon during the conversation, and if needed, we will provide suggestions for supporting the participant. The goals that are decided upon will be entered into a survey by study staff, and will be included in weekly emails to the supportive sponsor. After 8 weeks, we will reach out to the participant and supportive sponsor if the participant is stuck in lower levels of blue or bronze to determine if changes should be made to the original support goals. Participants without a supportive sponsor will not be excluded from study participation, and will complete a slightly modified version of the baseline and 8-week phone call, if necessary, in two-way conversations with study staff.

The intervention will end after 16 weeks, but participants will continue to receive a daily text message stating whether they achieved their step goal on the prior day during the 8 week follow-up period.

4.6. End-of-Study Questionnaire Completion

At the end of the 16-week intervention, patients will be alerted by the Way to Health platform to return to the website to complete an end-of-study questionnaire consisting of the San Diego Claudication Questionnaire, the Walking Impairment Questionnaire, the Patient-Reported Outcomes Measurement Information System (PROMIS) measures of mobility, pain interference, and satisfaction with social roles and activities, and the SF-36 physical functioning scale. Patients will complete the same questionnaire again 8 weeks later.

4.7. Subject compensation

Patients will be paid \$25 for enrolling in the study and completing baseline surveys, \$25 for completing the 16-week intervention with step count data available for $\geq 60\%$ of days and completing the 16-week survey, and \$25 for completing the study with step count data available for $\geq 60\%$ of days and completing the 24-week survey.

5. Statistical Methods

5.1 Primary and secondary outcome measures

The study's primary outcome measure will be change in daily step count from baseline to the intervention period for patients in the intervention arm versus patients in the attention control arm.

Secondary outcome measures will include:

- 1) Change in daily step count from baseline to the follow-up period
- 2) Change in daily number of minutes engaged in light, moderate, or vigorous physical activity from baseline to the intervention period, and from baseline to the follow-up period
- 3) Change in daily number of minutes engaged in moderate, or vigorous physical activity from baseline to the intervention period, and from baseline to the follow-up period
- 4) Change in Walking Impairment Questionnaire score from baseline to the end of the intervention period, and from baseline to the end of the follow-up period
- 5) Change in PROMIS mobility, pain interference, and satisfaction with social roles and activities scores from baseline to the end of the intervention period, and from baseline to the end of the follow-up period
- 6) Change in SF-36 physical functioning scale from baseline to the end of the intervention period, and from baseline to the end of the follow-up period

5.2. Sample Size

Patients with PAD walk approximately 3900 steps/day (SD 2689 steps).¹⁶ With a home-based exercise program, the mean change in steps/day over 4.5 months for patients with PAD was a decrease by 200 steps (SD ~2000 steps).¹⁶ By contrast, a gamification intervention similar to the one proposed increased step count by > 900 steps/day (SD ~2400 steps).¹⁹ With 100 patients (50 in each arm), the study will have 80% power to detect an 1100 step difference in change in daily step count between the two arms with alpha set at 0.05

5.3. Data Analyses

Data for all consented patients, whether or not they completed all protocol requirements, will be included for analysis. Patient demographics, risk profiles, clinical characteristics, and baseline questionnaire results will be reported. In addition to change in number of steps from baseline, secondary outcomes will include change in daily exercise minutes, and change the Walking Impairment Questionnaire, the Patient-Reported Outcomes Measurement Information System (PROMIS) measures of mobility, pain interference, and satisfaction with social roles and activities, and the SF-36 physical functioning scale. In exploratory analyses, we will identify baseline psychometric properties associated with greater change from baseline in daily steps, and greater response to the gamification intervention.

All analyses will be performed using intention-to-treat. Data can be missing for any day if the participant did not use the activity tracking device or did not upload data. For the main analysis, we will use multiple imputation for step values that are either missing or for values less than 1000 steps because evidence suggests these are not accurate measures of actual activity. We will perform five sets of imputations and results will be combined using Rubin's standard rules. We will perform sensitivity analyses to assess the robustness of the findings using only collected data with and without step values less than 1000 steps. The primary analysis will fit mixed effects

regression models to evaluate changes in physical activity outcomes measures adjusting for each participant's baseline step, time at the observation level using calendar month fixed effects, participant random effects, and adjusting for repeated observations of participant step counts. We will compare changes in daily step count and physical activity from baseline to the intervention period, excluding weeks 1-4 (the ramp-up period). We will repeat these analyses, comparing changes in daily step count and physical activity from baseline to the follow-up period. Secondary analyses will fit mixed effects regression models adjusted for other variables of interest such as participant characteristics. Exploratory analyses will fit mixed effects regression models to evaluate associations of participant characteristics or behaviors with strong or poor performance in the outcome measures. In a subgroup analysis, we will separately analyze subgroups reporting and not reporting exertional lower extremity symptoms.

For changes in survey measure scores from baseline to the end of the intervention, and from baseline to the end of follow-up, we will compare the intervention and control arms using paired t-tests, without adjustment for baseline characteristics.

6. Human Research Protection

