4.3. Determination of Baseline Step Count and Goal-Setting

Eligible participants will be mailed a wearable activity tracking device to wear for about two weeks to collect a baseline step count. They will also receive an email with baseline information about home-based exercise in PAD, including information about the benefit of walking in relieving PAD symptoms and improving functional capacity, and instructions for exercise in PAD.

The patients will be told to wear the device for two weeks to get accustomed to it. During this period, we will use a protocol from prior work to estimate a baseline step count using the second week of data. The first week of data will be ignored to diminish the tendency for use of devices in week 1 of receiving a new device to be significantly higher than what might be observed at steady state. To prevent risk of mismeasurement, we will ignore any daily values less than 1000 steps because evidence indicates these values are unlikely to represent capture of actual activity.^{27,28} At least four days of data must be available during that second week to estimate baseline measures; otherwise the period will be extended, and patients will be called to inquire if there are any issues with using the device. In prior work, we typically have 6 to 7 days of data from more than 90% of participants.²⁹ Participants who do not complete this run-in phase will not be randomized into the trial, nor will patients with step counts > 7500 steps/day during the run-in phase.

Once baseline measures have been established, eligible participants will be contacted to choose their goals using an approach we have found to work well in previous studies. They will be given their baseline step count and asked to select a step goal increase of 33%, 40%, 50% or choose a custom goal as long as it is at least 1500 steps greater than baseline. We have used this approach in the past because it gives participants the options of setting their own goal but also steers people to choose one of the options provided, any of which would be terrific from the standpoint of increasing physical activity. Leaving it completely open-ended risks having participants either pick goals that are ‘too easy’ or not likely to be attainable. In prior work, we find that on average participants chose ambitious goals and more than half selected a 50% step increase.

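### Do days below 1,000 steps need more handling than the imputation and the with/without sensitivity analyses already planned?

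*Combined protocol and SAP*

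**What the plan says.** Section 4.3 takes baseline from the second run-in week. It states that "we will ignore any daily values less than 1000 steps because evidence indicates these values are unlikely to represent capture of actual activity". It adds that "At least four days of data must be available during that second week to estimate baseline measures". When fewer are on hand, the run-in is lengthened and staff telephone the patient about the tracker.

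Section 5.3 applies the same cut-off after randomization: "we will use multiple imputation for step values that are either missing or for values less than 1000 steps". It then plans sensitivity analyses "using only collected data with and without step values less than 1000 steps". A day counts as missing when the tracker was not used or its data were not uploaded. No wear-time criterion appears. Baseline steps enter the primary mixed model as a covariate.

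Section 5.2 expects a mean of about 3,900 steps a day (SD 2,689). Section 4.4 has a randomization stratum below 2,500 steps.

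**The concern.** A 1,000-step cut-off backed by cited general evidence may not suit patients with PAD, for whom a day of 800 steps can be genuine. Four gaps seem to follow.

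- Both sensitivity analyses use collected data only, so none keeps low days while imputing days with no data.
- Section 4.3 defines one baseline, without low days. The version that keeps them could compare untrimmed follow-up with a trimmed baseline.
- No tabulation of low days by arm, period or stratum is planned.
- Section 4.3 does not say whether an ignored day counts toward the four-day minimum, which bears on who is randomized.

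The direction of any bias is not fixed. If low days are real and the intervention removes them, the main analysis understates the effect. If they are real and equally common in both arms, it overstates it. If they are partial wear, keeping them biases the result according to wear in each arm. Wear could differ by arm. Only intervention patients play for points ("each day the goal is not met, they are informed that they lost 10 points"), and only they may have a sponsor who receives weekly progress "including accumulated points, level in the game, and average step count". The planned results could then disagree without an explanation.

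**Working it through.** **Yardstick.** Section 5.2 claims 80% power for 1,100 steps with 50 per arm and alpha 0.05 (two-sided assumed). With SD 2,000, SE = 2,000 × √(2/50) = 400, and power = Φ(1,100/400 − 1.96) = Φ(0.79) = 78.5%. That reproduces the claim closely, so 400 steps is the scale used below.

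**Are real low days plausible?** Taking 2,689 as a between-person SD, the share of patients averaging below 1,000 is Φ((1,000 − 3,900)/2,689) = Φ(−1.08) = 14.0% under a normal distribution and 3.1% under a log-normal. So yes.

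**What the planned analyses separate.**

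| | Low days out | Low days kept |
|---|---|---|
| No-data days imputed | main analysis | not planned |
| Collected data only | planned | planned |

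The two cells in the lower row differ only in the 1,000-step rule. The two in the left column differ only in imputation. Both factors are isolated without the empty cell. That cell would add only whether the rule acts differently once no-data days are imputed.

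**Size if all low days are real.** The documents give no daily distribution, so these are assumptions: log-normal or gamma person means, day-to-day CV 0.3 to 0.7, 7 baseline days, 84 days in weeks 5–16, changes of −200 and +900 (additive or proportional), linear adjustment for baseline, and exclusion of low days standing in for imputation. There were 40,000 simulated patients per scenario. Selected results for the adjusted arm difference:

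| Scenario | Truth | Main | Low days kept, 4.3 baseline | Low days kept, recomputed baseline | Trimmed minus full baseline |
|---|---|---|---|---|---|
| log-normal, CV 0.3, proportional | 960 | 946 | 960 | 961 | 3,395 − 3,379 = 16 |
| log-normal, CV 0.5, additive | 1,110 | 1,037 | 1,110 | 1,111 | 3,438 − 3,368 = 70 |
| gamma, CV 0.5, additive | 1,101 | 1,030 | 1,101 | 1,101 | 3,608 − 3,540 = 68 |
| log-normal, CV 0.7, additive | 1,105 | 990 | 1,105 | 1,106 | 3,567 − 3,387 = 180 |
| log-normal, CV 0.7, proportional | 978 | 904 | 978 | 985 | 3,568 − 3,385 = 183 |

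Across all scenarios the main analysis is 14 (960 − 946) to 115 (1,105 − 990) steps low, and 115/400 = 0.29 SE at most. In these scenarios the planned version that keeps low days recovers the truth with either baseline. The baseline choice moves the arm difference by at most 985 − 978 = 7 steps. Baseline is fixed before randomization and is a covariate, so the mismatch shifts change from baseline by about the same amount in both arms.

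**Size if low days are partial wear.** In the same model (log-normal, CV 0.5, additive), with 5% of days partly worn in both arms, keeping low days gives 1,054 and the main analysis 1,035, against a truth of 1,106. With 15% the figures are 937, 1,036 and 1,104.

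For unequal wear, let each partial day record 400 steps, let m be mean baseline steps (3,389 to 3,587), and let p_c and p_i be the partial-wear shares in control and intervention. For a true effect of 1,100, keeping low days gives (1 − p_i)(m + 1,100) + 400p_i − [(1 − p_c)m + 400p_c].

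- 5% and 5%: 0.95 × 1,100 = 1,045.
- 5% control, 2% intervention: 0.03m + 1,066 = 1,168 to 1,174.
- 10% control, 5% intervention: 0.05m + 1,025 = 1,194 to 1,204.
- 2% control, 5% intervention: 1,057 − 0.03m = 949 to 955.

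**Would a table by stratum settle which it is?** Real low days should cluster in the stratum below 2,500. So would partial wear if a partly worn day records a random (uniform) fraction of that day's steps. The chance of falling below 1,000 is then 1,000/x for a day of x steps: 1,000/2,000 = 50%, but 1,000/6,000 = 17%. Averaged over the modelled patients (CV 0.3 to 0.5), it is about 60–67% below 2,500 and 18–23% above 5,000. Pure artefact thus gives roughly a threefold gradient. By arm, fewer low days under the intervention fits both better walking and better wear.

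**Run-in count.** Section 4.3 discards low values and then asks for four days with which to estimate baseline. The natural reading is that discarded days do not count. On that reading a patient averaging 1,000 steps misses four days in a fraction f = 0.587 to 0.643 of weeks. With extension and independent weeks, 1 − f² = 59–66% qualify within two weeks and 1 − f³ = 73–80% within three. All this precedes randomization.

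**The case for a change.** The strongest case for a change is that it is cheap: a few sentences, one table and one imputation run, with the primary analysis untouched. The version that keeps low days differs from the main analysis in two respects at once. Under differential wear the two definitions differ by −127 to +166 steps, and nothing planned explains why. Section 5.1 frames the outcome as change from baseline, and a within-arm artefact of 16 to 183 steps is not trivial beside the 200-step fall cited in 5.2. If low days are real and equally common (400 steps on 10% of days in both arms), the truth is 0.9 × 1,100 = 990 while the main analysis reads 1,036 to 1,079, which is 5–9% high.

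Part of this stands. Real low days are plausible, the plan cannot tell them from partial wear, and the text is silent on the baseline for that version. But comparing through the collected-data analysis without low days separates the two factors. The mismatch is inferred from silence and touches only within-arm change in one sensitivity analysis, whereas the primary outcome compares arms. The larger figures rest on wear rates chosen for illustration. The proposed table would not reliably supply the missing explanation.

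**Conclusion.** No change is called for. The threshold is a stated choice, applied alike at baseline and in the main analysis, and the plan already tests it with a pair of analyses that differ only in that rule. With all low days real, the main result moves by about 14 to 115 steps (up to 0.29 SE), and the planned version that keeps them shows it. The baseline mismatch is worth at most 7 steps on the arm difference. These sizes rest on assumed step distributions, day-to-day variation and wear rates, none of which the documents give.

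No proposed addition would alter the primary analysis or the between-arm conclusion, or reliably show whether low days are real. Three details remain open: the baseline used when low days are kept, whether ignored days count toward four, and how often low days occur in each arm. Competent analysts would match the baseline to the rule, read the four-day minimum as four usable days, and report the counts as description.

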6.3 Subject privacy

Interested participants will be directed to the Way to Health portal where they will be asked to enter data related to eligibility and their demographic characteristics. Enrollment will include a description of the voluntary nature of participation, the study procedures, risks and potential benefits in detail. The enrollment procedure will provide the opportunity for potential participants to ask questions and review the consent form information prior to making a decision to participate. Participants will be told that they do not have to answer any questions if they do not wish and can drop out of the study at any time, without affecting their medical care or the cost of their care. They will be told that they may or may not benefit directly from the study and that all information will be kept strictly confidential, except as required by law. Subjects will have access to a copy of the consent document. All efforts will be made by study staff to ensure subject privacy.

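### Five imputations with no fixed seed may leave the primary step-count result noticeably seed-dependent if about 10% or more of patients have no data in weeks 5-16

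*Combined protocol and SAP*

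**What the plan says.** All of this is in the combined protocol and SAP.

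- **Number of imputations (5.3):** "We will perform five sets of imputations and results will be combined using" Rubin's rules. No reason for five, no seed, no check of Monte Carlo error and no rule for raising the number is given.
- **What is imputed (5.3):** "we will use multiple imputation for step values that are either missing or for values less than 1000 steps". The imputation model is not described.
- **Who is analysed (5.3):** "Data for all consented patients, whether or not they completed all protocol requirements, will be included for analysis". The analyses are by intention to treat, and a day's value may be missing because the tracker was not worn or its data were not uploaded.
- **Window (5.3):** the main comparison leaves out the four ramp-up weeks of the 16-week intervention, so it covers weeks 5-16, that is 12 x 7 = 84 days.
- **Leaving the study (6.3):** participants "can drop out of the study at any time".
- **Completeness (4.3):** in prior work, "we typically have 6 to 7 days of data from more than 90% of participants". This describes the baseline week, not weeks 5-16.
- **Sensitivity analyses (5.3):** "using only collected data with and without step values less than 1000 steps". Neither of these varies the number of imputations.

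**The concern.** A multiple-imputation estimate carries random error from the imputation draws on top of sampling error. That extra error shrinks with the number of imputations and grows with the fraction of missing information. Five is ample when a patient's missing days are surrounded by that patient's own observed days. It is few when some patients contribute nothing to the window, because their whole mean for weeks 5-16 is then drawn from the model.

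The plan allows that situation and does not say how common it will be. If it is common enough, the same data and the same model run under another seed could move the primary estimate by a visible amount. For a result near the 0.05 threshold, the verdict could change. Fixing a seed makes the number repeatable, but only more imputations make it less arbitrary.

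**Working it through.** **Inputs from section 5.2:** 50 patients per arm, a target difference of 1100 steps, alpha 0.05, and SDs of change of about 2000 (home-based exercise) and 2400 (gamification).

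**Assumed inputs (not in the documents):** the share of patients with no data in weeks 5-16, and an imputation model with a patient-level effect.

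**1. The plan's own figure.** With SD 2000, SE = 2000 x sqrt(2/50) = 400. Two-sided power is about Phi(1100/400 - 1.96) = Phi(0.79) = 78.5%, close to the stated 80%. So SE 400 is a fair base. With both SDs (2000 and 2400) the SE is 442, which makes the seed effects in steps about 10% larger.

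**2. From missing patients to missing information.** Let FMI be the fraction of missing information. A simulation with 50 per arm, SD 2000 and 20% of days missing at random places gave FMI 0.002, 0.054, 0.105 and 0.210 when 0%, 5%, 10% and 20% of patients had no data. So FMI is close to the share of patients without data.

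**3. Seed-to-seed SD.** With m imputations the SE is 400/sqrt(1 - FMI), and the seed SD of the estimate is SE x sqrt(FMI/m).

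| FMI | SE | Seed SD, m=5 | Seed SD, m=50 |
|---|---|---|---|
| 0.05 | 410 | 410 x 0.100 = 41 | 410 x 0.032 = 13 |
| 0.10 | 422 | 422 x 0.141 = 60 | 422 x 0.045 = 19 |
| 0.20 | 447 | 447 x 0.200 = 89 | 447 x 0.063 = 28 |

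**4. Effect on the verdict.** Rubin's rules were simulated in 400,000 trials with a true difference of 1100, complete-data SE 400 and two seeds per trial.

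| FMI | Opposite verdicts at 0.05, m=5 / m=50 | Power, m=5 / m=50 |
|---|---|---|
| 0.05 | 3.8% / about 1.1% | 75.9% / 76.4% |
| 0.10 | 6.2% / 1.8% | 73.0% / 74.1% |
| 0.20 | 11.3% / 3.0% | 66.1% / 69.0% |

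By formula, the confidence interval with m=5 is 1.2% (FMI 0.10) to 2.9% (FMI 0.20) wider than with m=50.

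**5. Where it bites.** If the observed-data p-value is 0.03, about 16% of seeds (10% of patients without data) or 27% (20%) give p of 0.05 or more with m=5. With m=50 it is 1% or fewer. If the observed difference is exactly 1100 steps, p stays below 0.05 in 99.7% and 89% of seeds even with m=5.

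**6. Scattered missing days only.** With 10-40% of days missing and an assumed within-patient daily SD of 1500-3000, FMI is below 0.02 and the seed SD at m=5 is 5-24 steps.

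**7. How many are enough.** For a seed SD of at most 5% of the SE, FMI/m must be at most 0.05^2 = 0.0025, so m is at least 400 x FMI. That is 24 at 6% of patients without data, 40 at 10% and 80 at 20%.

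**The case against.** **The rate may be low.** Patients who do not complete the run-in are not randomised (4.3). Anyone for whom six months is not feasible is excluded (3.3.2). Two of the three payments require step data on at least 60% of days (4.7). These features bear on the rate, but they do not fix it, and the only completeness figure concerns a baseline week. What stands is that the size is conditional. Shares of 30-40% without data would be extremes and should not carry the argument.

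**The model is unspecified.** If days were drawn independently with no patient effect, the draws would average out over 84 days. The seed SD at m=5 would be only about 6-16 steps with 5-10 fully missing patients per arm. This stands as a limit on the figures, although such a model would understate the between-imputation variance.

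**A seed-free check exists.** The planned analysis of collected data without values below 1000 uses the same observed days with no imputation. It can show that the main result looks odd, but it does not make the main result less seed-dependent.

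**The efficiency loss is small.** Relative efficiency with five imputations is 98% at FMI 0.10 and 96% at 0.20. Most of the lost power comes from the missing data: 78.5 - 74.1 = 4.4 points at FMI 0.10, against 1.1 points from using five rather than 50. This also stands.

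**Stronger readings.** A reader might infer that five imputations bias the primary estimate or invalidate the inference. They do not: Rubin's rules allow for a finite number of imputations. A reader might also infer that another imputed analysis is needed that keeps recorded values below 1000. The planned collected-data pair already shows the effect of that cut. In 15 simulated scenarios, the keep-versus-cut gap differed by at most about 2 steps between collected and imputed data, so the extra run would add nothing useful.

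**Conclusion.** The point holds as a low-cost improvement, and its size is conditional. With scattered missing days, or about 5% or fewer of patients without data in weeks 5-16, five imputations are adequate or nearly so.

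The figures for 10-20% rest on three assumptions: that share of patients, a patient-level effect in the imputation model, and a complete-data SE of 400. At the upper end, the seed SD of 89 steps is 89/1100 = 8% of the target difference and comes from the random number generator alone.

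A result far from 0.05 keeps its verdict. The documents do not support saying that the problem will occur, only that the plan permits it and has no safeguard against it.

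**What to change.** In section 5.3, replace the five imputations with at least 50 and state the seed in advance. Add a rule: after the run, compute the Monte Carlo SD of the treatment difference, sqrt(B/m), where B is the between-imputation variance. If it exceeds about 5% of the SE, raise the number of imputations until it does not. That would take about 80 if 20% of patients have no data in the window.

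No additional analysis of values below 1000 is needed, and the two planned collected-data analyses stay as they are. The cost is computing time only. Data collection, eligibility and strata are unchanged. If missing days prove to be only scattered, the gain is negligible and so is the cost.
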